2 INTRODUCTION: BACKGROUND INFORMATION AND SCIENTIFIC RATIONALE

2.1 Background and Rationale

Trichiasis is an important cause of blindness in developing countries with limited access to water and sanitation measures. The disease primarily affects adult women, although in areas where trachoma is highly-endemic, trichiasis is occasionally diagnosed in young children. Surgery is available to correct trichiasis, but long-term success rates are suboptimal in many settings. Two primary surgical procedures are used, bilamellar tarsal rotation (BLTR; bilamellar) and posterior lamellar tarsal rotation (PLTR), also known as Trabut.

Surgical Procedure Comparison

A recent trial conducted in the Amhara region of Ethiopia compared BLTR and Trabut and found a significant reduction in post-operative trichiasis following Trabut as compared to BLTR (22% vs. 13%; Adjusted Odds Ratio 1.96; 95% CI: 1.40-2.75). The trial employed Trabut-trained surgeons who received conversion training to perform BLTR. Each surgeon performed both procedures as part of the trial. The trial was exceptionally well run, and some programs are now strictly training surgeons with Trabut. However, there is much debate over whether the trial results are broadly applicable for experienced surgeons who were first trained in BLTR and for newly trained surgeons. Specifically, since the release of the trial results, two meetings of the global trichiasis community have been held (one a WHO-sponsored meeting of trichiasis experts and the other the annual program review of the organization performing the largest volume of trichiasis surgeries worldwide, which included global experts from most trachoma-endemic countries). At both meetings, experts strongly recommended that another trial should be conducted which utilizes BLTR surgeons who receive conversion training to Trabut. Additionally, [name] is a member of the planned trials and has indicated strong in-country support for the need for an additional study to examine this question. In the planned trial, we will compare post-operative trichiasis rates for surgeries performed with each of these procedures. Surgeons will be either newly trained in both procedures or will be BLTR surgeons who have received conversion training in Trabut and have performed at least 100 Trabut surgeries.

Incision Height Comparison

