4.4 Treatment Assignment Procedures

4.4.1 Randomization Procedures

Participants will be randomized at the participant level to one of three arms: 1) BLTR with target incision height of 3 mm 2) BLTR with target incision height of 5 mm and 3) Trabut with target incision height of 3 mm. Both eyes will be operated with the same surgical procedure and incision height if both eyes need surgery. Randomization assignments will be prepared in individual opaque envelopes with the patient ID number on both the outside of the envelope and on the internal papers indicating the arm assigned. The envelope will be opened during enrollment by the Program Manager. The surgeon and surgical assistant will both confirm the assigned surgical procedure and incision height at the start of the procedure. They will be required to indicate the assigned procedure and height on the surgical evaluation form and to measure and record the actual height of the incision made. Incision heights will be measured for patients in all three randomization arms.

The randomization assignments will be developed at UNC. Each week reported assigned surgical procedures and incision heights will be compared against the master table to ensure the assigned procedure and heights are consistently being reported for each participant. Details on monitoring are available in the quality assurance section.

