5.3 Assessment of Clinician and/or Subject Compliance with Study Procedural Intervention

The Project Director will regularly monitor surgical activities in-person to ensure that the surgeons are following the study procedures, performing the correct procedure, and accurately measuring and recording the incision height. Each week the Coordinating Center (CC) will compare the assignment reported on the Surgical Evaluation form against the actual assignment. The CC will issue a query for each instance where there is any disagreement between the recorded assignment and actual assignment. The CC will also compare the reported assigned height on the Surgical Evaluation against the actual height measurements. Frequency of differences greater than 0.5mm will be reported at the surgeon level on a cumulative basis. Whenever more than 5% of the actual measurements are more than 0.5 mm different than the assigned measurements, the surgeon will be reevaluated by one of the study ophthalmologists to determine what corrective measures need to be made.

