6.2 Baseline Ocular Exam and Surgery (Day 0)

The baseline exam occurs immediately after enrollment and just prior to surgery (all happen on the same day). The goal of this exam is to characterize trichiasis severity and visual acuity prior to surgery. Baseline trichiasis severity is an important predictor of post-operative trichiasis; hence, these data will be included in all models evaluating the outcome.

After the ocular exam, the patient receives trichiasis surgery.

Required Data Collection:

- Baseline Ocular Exam Form
- Surgical Evaluation Form

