9.3 Analysis Plan

We will follow these general analysis principles:

- The primary analyses will be performed according to the participant's assigned intervention.
- All participants who complete randomization and have surgery performed will be included in analyses.
- All events following surgery will be counted.
- All analyses will be conducted at the eye level, using the generalized estimating equations approach to correct standard errors (to account for the correlation between two eyes of a subject).
- Unless otherwise indicated, three sets of analyses will be performed: 1) BLTR 3 mm versus BLTR 5 mm and 2) BLTR 3 mm versus Trabut 3 mm 3) BLTR 5 mm versus Trabut 3 mm.

Post-operative Trichiasis Analyses:

The primary analyses will be based on the dichotomous outcome: presence or absence of post-operative trichiasis at any time point within 12-18 months following surgery. Both unadjusted and adjusted analyses will be performed. Adjusted analyses will account for the severity of pre-operative trichiasis, with severity defined based on the table below.

Trichiasis Severity Classification	Description
Mild	1-4 Eyelashes touching globe, no epilation OR 1-10 Eyelashes epilated, no eyelashes touching globe

Moderate	5-9 Eyelashes touching globe, no epilation OR 1-4 Eyelashes touching globe and 1-10 eyelashes epilated
Severe	5-9 Eyelashes touching globe and 1-10 eyelashes epilated OR 10+ Eyelashes touching globe, regardless of epilation status OR 11-20 Eyelashes epilated, regardless of eyelashes touching globe OR Entire eyelid epilated

(Gower et al. 2013. *JAMA Ophthalmol.*;131(3):294-301.)

Multiple secondary analyses of post-operative trichiasis will be performed. We will compare the severity of post-operative trichiasis between groups, with severity defined using the table above. First, we will compare the primary groups utilizing severity at first observation (6 weeks or 12 months for the primary outcome). Then we will compare groups using severity at final observation. This will allow us to determine whether one group has a higher ‘surgical failure’ rate and whether recurrent trichiasis progression varies across interventions. We will conduct both unadjusted and adjusted analyses.

Eyelid Contour Abnormalities:

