Primary analyses of eyelid contour abnormalities will be based on a dichotomous variable: presence or absence of moderate/severe contour abnormality at the last study visit where the participant was seen between 6 weeks and 12-18 months, , or at last visit before repeat surgery using the photograph grade, which will be based on the definitions below. For the purposes of this analysis, mild will be combined with “no abnormality” and moderate and severe will be combined to form the “moderate/severe contour abnormality” group.

Abnormality	Definition
Mild	Vertical deviation from the natural contour, 1 mm in height (less than half the pupil height in daylight) and affecting 1/3 of horizontal eyelid length
Moderate	Vertical deviation from the natural contour 1–2 mm in height (about the pupil height in daylight) or affecting 1/3–2/3 of horizontal eyelid length
Severe	Vertical deviation from the natural contour 2 mm in height (more than the pupil height in daylight) or a defect >2/3 of the horizontal eyelid length

(Gower et al. 2012 *PLoS Negl Trop Dis* 6(6): e1713)

Secondary analyses will explore the relationship between incision height and the full range of eyelid contour abnormalities, which will require use of the photographic grade that will be graded centrally.

Targeted versus Actual Incision Height:

We will conduct an analysis to compare the assigned incision height against the actual incision height measured during surgery. If more than 10% of the heights vary by more than 0.5 mm, we will conduct secondary analyses for each of the above analyses to determine whether the results of the actual incision height analyses are similar to the per-protocol analyses. If differences exist, we will report these analyses separately, but will emphasize that the per-protocol analyses are the primary analyses.

New Versus Conversion Surgeons

Analyses will also be conducted stratifying based on surgeons' prior experience. Specifically, we will conduct all above analyses based on whether surgeons were trained on both bilamellar and Trabut simultaneously, or whether they first learned bilamellar and received additional training in Trabut at a later time.

1-day Surgical Corrections

Finally, we will conduct an analysis to determine whether there is a difference in the rate of 1-day surgical corrections by study arm.

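### The new-versus-conversion surgeon analysis gives results by training group but no estimate of whether the BLTR-versus-Trabut effect on post-operative trichiasis differs between the groups (low priority)

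*Combined protocol and SAP*

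**What the plan says.** Section 9.3, under New Versus Conversion Surgeons, plans analyses stratified by the surgeon's prior experience: "we will conduct all above analyses based on whether surgeons were trained on both bilamellar and Trabut simultaneously", or learned bilamellar first and added Trabut later. That is the whole plan on this topic.

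The two groups come from section 2.1: "Surgeons will be either newly trained in both procedures or will be BLTR surgeons who have received conversion training in Trabut". The same section gives the motive. After the earlier BLTR-versus-Trabut trial there was "much debate over whether the trial results are broadly applicable for experienced surgeons who were first trained in BLTR and for newly trained surgeons".

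Three other statements bear on the point:

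- Section 4.4.1 on allocation: "Participants will be randomized at the participant level to one of three arms". Surgeon training is not allocated.
- Section 9.3 on correlation: analyses are at eye level, "using the generalized estimating equations approach to correct standard errors (to account for the correlation between two eyes of a subject". Clustering by surgeon is not mentioned.
- Section 6.2 on baseline trichiasis severity: "hence, these data will be included in all models evaluating the outcome". Section 9.3 also adjusts for severity, and the protocol summary adds demographic characteristics. Neither includes surgeon training.

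Neither the objectives (3.1), the hypotheses (9.1), the sample size (9.2) nor the analysis plan (9.3) names an arm-by-training term, a ratio of effects or a test of heterogeneity.

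**The concern.** The subsection title sets new surgeons against conversion surgeons, and section 2.1 gives readers a reason to make that comparison. Two sets of within-group results do not in themselves estimate the difference between the groups. With no such estimate planned, the easiest reading is to note that the effect is significant in one group and not in the other. That happens often when the true effect is the same in both, because each group has fewer eyes than the whole trial.

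At stake is the reading of a supplementary analysis: a report could suggest that the choice between BLTR and Trabut depends on how the surgeon was trained when the data do not show it. The reverse error is also possible, if two similar-looking results are taken as proof of equal effects.

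**Working it through.** The plan has no figure for this analysis, so the check starts from its sample size.

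**The plan's own figure.** The later steps of the 9.2 table reproduce for 15% and RR 0.75: 1098 × 3 = 3294; × 2 = 6588 surgeries; 3294 × 1.4 = 4612 at 40% bilateral; shortfall 1976 / 1.4 = 1411; 3294 + 1411 = 4705; 4705 / 0.95 = 4953. The starting 1098 does not follow from the listed 5% two-sided alpha and 80% power, which give 1272 eyes × 1.24 / 2 = 789. That is a separate matter; 4,953 is taken here as planned.

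**Inputs from 9.2:** 4,953 participants, three equal arms, 5% loss, 40% bilateral, between-eye correlation 0.24, 15% PTT with BLTR 3 mm, 25% reduction to 11.25%. **Assumed:** the split of surgeries by training, 50/50 or 30/70, since the documents give none.

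**Effective eyes per arm.** 4953 / 3 × 0.95 = 1,568 participants; × 1.4 = 2,196 eyes. Variance inflation is (0.6 + 0.8 × 1.24) / 1.4 = 1.137. Effective eyes: 2,196 / 1.137 = 1,931.

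**Effect.** Odds ratio (0.1125/0.8875) / (0.15/0.85) = 0.718, so the log odds ratio is 0.331 in size.

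**Standard error in a training group** with n effective eyes per arm: sqrt(1/(n × 0.1275) + 1/(n × 0.0998)), where 0.1275 = 0.15 × 0.85 and 0.0998 = 0.1125 × 0.8875. Power is approximately Φ(0.331/SE − 1.96).

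| Split | n per arm | SE | Power |
|---|---|---|---|
| 50/50 | 965.5 in each | 0.136 | 0.682 in each |
| 30/70 | 579 and 1,352 | 0.176 and 0.115 | 0.470 and 0.821 |

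**Exactly one group significant, identical true effect.**

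- 50/50: 2 × 0.682 × 0.318 = 0.434
- 30/70: 0.470 × 0.179 + 0.821 × 0.530 = 0.519

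**At least one of the two Trabut contrasts discordant,** if BLTR 5 mm and Trabut are both at 11.25%. The null contrast is discordant with probability 2 × 0.05 × 0.95 = 0.095. Treating the contrasts as independent:

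- 50/50: 1 − 0.566 × 0.905 = 0.488
- 30/70: 1 − 0.481 × 0.905 = 0.565

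That is about 49% and 57%. Simulation of 400,000 trials that keeps the shared Trabut arm gives 0.482 and 0.566, so the overlap matters little.

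**What an interaction estimate would deliver.**

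- SE of the log ratio of odds ratios: sqrt(0.136² + 0.136²) = 0.192 at 50/50 and sqrt(0.176² + 0.115²) = 0.210 at 30/70. The 95% CI is the estimate times or divided by exp(1.96 × SE), that is 1.46 or 1.51.
- False rejection: 5% per contrast. For at least one of two it would be 1 − 0.95² = 9.75% if they were independent; with the shared arm it is about 9%.
- Power for RR 0.75 in one group and 1.0 in the other at 50/50: SE = sqrt(3/(965.5 × 0.1275) + 1/(965.5 × 0.0998)) = 0.186, and Φ(0.331/0.186 − 1.96) = 0.43. At 30/70 the SE is 0.206 or 0.201, depending on which group has the effect, and power is 0.36 or 0.38.

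These are unadjusted approximations that ignore variation between surgeons, so the power figures are upper values.

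**The case against.** The strongest reply is that the plan answers the question it asks. Section 2.1 asks whether the earlier result applies to BLTR-first surgeons and to newly trained ones, and that needs the effect within each group. No objective or hypothesis asks whether the effect differs. This stands, and it is the main reason the point is low priority.

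Second, the discordance figures describe an inference that the plan does not state. This also stands. A reader might infer that the sponsor intends to compare the groups by significance; no section says so. The figures show what that habit would cost, and they are not an error rate of the planned analysis.

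Third, the ratio of odds ratios can be derived from the two group results, and its power is low. Both are true. What remains is the gain from pre-specification: the ratio is reported whatever it shows, with an interval that makes the imprecision visible.

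Fourth, stratifying might mean one pooled estimate stratified by training. That reading gives no estimate of the difference either.

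A reader might also infer that ignoring surgeons invalidates the analysis, or that a surgeon-clustered repeat with a fixed t reference should be required. The documents give neither the number of surgeons nor the between-surgeon variance. The size of any effect on the standard errors is therefore unknown, and whether such a repeat is workable cannot be judged. A caution about the interval is as far as the text allows.

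**Conclusion.** The omission is real and narrow. The plan gives effects within each training group but neither an estimate of how the BLTR-versus-Trabut effect on PTT differs between them nor a rule for judging a difference.

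The numbers rest on the assumed 50/50 or 30/70 split and the planning rates in 9.2. The figure for the pair of contrasts also assumes that BLTR 5 mm and Trabut share a rate of 11.25%. On that basis, reading by significance would mislead in about 43% to 52% of trials per contrast, and in about 49% to 57% for at least one of the two Trabut contrasts.

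Adding the 3 mm versus 5 mm BLTR contrast would raise the figure to 66% to 74%. A reader might infer that this larger range is the size of the problem, but the debate in section 2.1 concerns BLTR against Trabut, so the two Trabut contrasts are the relevant ones.

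Nothing here affects the primary analysis or the trial's size.

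**What to change.** In section 9.3, keep the odds ratios with 95% CIs within each training group for all the planned outcomes. For PTT only, add training and an arm-by-training interaction to the planned adjusted GEE model, with the same covariates as the primary adjusted analysis, for BLTR 3 mm versus Trabut and BLTR 5 mm versus Trabut. Report each ratio of odds ratios with its 95% CI, labelled exploratory.

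State also that:

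- a difference by training will be judged from this estimate, not from significance in one group only;
- a null interaction does not show equal effects;
- training is a non-randomised, surgeon-level factor, so the CI may be too narrow, because the GEE accounts only for the two eyes of a subject.

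The cost is a few sentences and two models. No new data are needed, since the stratification already requires each surgeon's training group. The downside is limited power, at most about 43% for RR 0.75 versus 1.0 (36% to 38% at 30/70), and about a 9% chance of at least one p < 0.05 across the two terms when no difference exists.

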10 QUALITY CONTROL AND QUALITY ASSURANCE

We will ensure high quality data collection through the course of the trial by ensuring adequate training of all staff on human subjects research and their roles in the trial. All staff must be certified in their respective roles by the project leaders before interacting with study participants and handling study-related data.

10.1 Training

All personnel will undergo extensive training to ensure consistency in data-collection procedures. We will begin with an ethics training session for all study staff, and ethics certification will be required from each staff member before the study begins. We will then provide an overview of the study design, each team member's responsibilities, and how members integrate to form a cohesive data-collection team. Then, a two-day training session will be held for each data-collection group to ensure they understand forms completion and the details of the data that they are supposed to collect.

The recruitment team, surgical assistants, and study coordinators will be trained on appropriate methods for conducting in-person interviews and use of the data-collection forms. Training for all personnel will include didactic instruction and clinical demonstration with live subjects. Upon completion of training, all personnel will be evaluated for all procedures that they will be asked to perform. Only those who pass certification will continue with the study team.

An independent evaluator will critically examine all surgeons to ensure that they perform high-quality surgery and follow recommended WHO procedures. Each surgeon will be evaluated using the WHO certification checklist and only certified surgeons will be allowed to participate in the study. [name] will train the surgeons on how to consistently measure incision heights and incision lengths. We will require $\kappa > 0.7$ for each measurement comparing the individual surgeon to [name] before the surgeon will be considered proficient in collecting these measures.

The outcomes examiner will be trained on how to grade trichiasis and eyelid contour abnormalities using photographs and actual trichiasis patients. κ of 0.7 will be required before the examiner is certified. In the second year of the trial, recertification for all patient examiners will be held at the start of the second series of surgical camps and 12-month follow ups.

10.2 Quality Monitoring

To ensure data integrity and study participants' safety, our plan for data and safety monitoring involves several levels. The first level is the extensive set of data-management activities (see Protocol and Manual of Procedures) to help ensure data integrity. These include daily field-based review of data collection to ensure completeness and accuracy before submitting the data to the data entry team, redundant systems to check randomization schemes, double data-entry practices, and

continuous data-quality monitoring through generation of regular reports. These reports are reviewed by the data manager to initiate data cleaning operations, and by the Principal Investigator, who may initiate re-training exercises or change supervisory practices as needed.

The second level of monitoring includes regular site visits by our senior study team members. Our team of experts will ensure all staff members are proficient in necessary procedures before the study begins. During recruitment, Drs. [name] and [name] will alternate making monthly visits to the study team to monitor surgical procedures and correct any drift or modifications that have inadvertently arisen. At the start of the 6-week and 12-month visits, [name] will return to Ethiopia to evaluate the outcomes assessor and ensure kappas are at least 0.7 for key outcomes (PTT and ECA). [name] also will visit Ethiopia at the start of 12-month data collection to provide refresher training to all study team members and to monitor data-collection procedures.

10.3 Data and Safety Monitoring Board

With input from NIH, we will assemble a data and safety monitoring board (DSMB) to oversee the study. At a minimum, the committee will consist of a trialist, a statistician, and content experts, including someone with local cultural expertise. We will plan for one DSMB meeting prior to study initiation, and then in-person meetings annually, with at least one scheduled teleconference between in-person meetings, and more as needed or desired by the DSMB. We will prepare summary reports of accumulated data for each meeting.

11 ETHICS/PROTECTION OF HUMAN SUBJECTS

11.1 Ethical Standards

The investigators will ensure that this study is conducted in full conformity with the principles set forth in the Declaration of Helsinki and The Belmont Report: Ethical Principles and Guidelines for the Protection of Human Subjects of Research, as drafted by the US National Commission for the Protection of Human Subjects of Biomedical and Behavioral Research (April 18, 1979) and codified in 45 CFR Part 46 and/or the ICH E6.

